3. EGA
4. Name of obstetrician performing ECV procedure
5. Presence of inflated Fetal Pillow
6. Presence of terbutaline
7. Presence of palpable fetal head
8. Estimated fetal weight (kg)
9. Fetal head position *confirmed by ultrasound
10. Fetal back position
11. Position of fetal neck
12. Location of placenta
13. Amniotic fluid index (4 quadrant total)
14. Fetal station (-3 through +3)
15. Maternal cervical dilation (cm)
16. Presence of rupture of membranes within 1 hour of procedure
17. Presence of 3 or more contractions in 10 minutes immediately prior to procedure
18. Bleeding equal to a menstrual period during or within 1 hour of the ECV procedure.
19. Development of a pelvic hematoma during or within 1 hour after the ECV procedure.
20. Development of a vaginal laceration during insertion of the device, the ECV procedure, or removal of the device.
21. Presence of fetal bradycardia
22. Presence of fetal heart rate decelerations
23. Presence of delivery within 1 hour of procedure
24. VAS pain score immediately prior to ECV (-3 minutes)
25. VAS pain score immediately after insertion of Fetal Pillow (+ 2 minutes)
26. VAS pain score after inflation/sham inflation (+ 1 minute)
27. VAS pain score immediately after each ECV procedure attempt, maximum of 4 attempts (+ 2 minutes)
28. Total number of attempts
29. Procedure successful Y N (Primary Outcome) *confirmed by ultrasound
30. Fetal head position post ECV *confirmed by ultrasound
31. Number of forward rolls
32. Number of reverse rolls
33. Note which procedure was successful

34. Did patient request to have spinal or epidural anesthesia after initiation of ECV procedure (off of study protocol): Y N
35. Presence of regional anesthesia prior to ECV procedure (Excluded from study)
36. Length of time from start of procedure to hospital discharge
37. Cost of hospital stay for ECV procedure

Study Design

Research Design

This is a prospective, randomized double-blind clinical trial evaluating the effect of a balloon device to elevate the fetal buttocks during external cephalic version procedures. Eligible study population: pregnant women between 37-40 weeks estimated gestational age with a breech presenting baby and no contraindications to ECV.

Study Agent, Device, and/or Intervention Description:

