The Safe Obstetric Systems Inc. Fetal Pillow is a sterile balloon device that comes in a sterile, single-use package (please see attached information). The Food and Drug Administration (FDA) has reviewed this device and determined it to be Non-Significant risk (NSR) because it does not meet the definition of a significant risk (SR) device under 21 CFR 812.3(m) of the investigational device exemptions (IDE) regulation (21 CFR 812). The device will be provided at no charge to AdventHealth Orlando. Drs. [name] or [name] will place the pillow into the vagina then the pillow will either be inflated/sham inflated by the midwife/physician with sterile saline in order to raise the fetal presenting part. After the procedure the device is deflated, removed and discarded. The Fetal Pillow device will be stored in a climate-controlled, locked storage area in the women's hospital accessible to the study investigators, midwife/physician and research personnel. It is possible that the manufacturer of this device may report de-identified study data to the FDA at a later date.

Study Site/Location and Number of Subjects

- AdventHealth Orlando.
- Estimated number of subjects: 138

Multi-Site Research Logistics/Communication Plan: N/A

Research Conducted in a Foreign Country: N/A

Community-Based Participatory Research: N/A

Subject Selection

Vulnerable Populations:

While the study population consists solely of pregnant women (some of whom may be AdventHealth Orlando employees), this research is unlikely to present more than minimal risk to subjects. This device has been used successfully to elevate the fetal head during difficult cesarean deliveries, and is FDA approved for this indication. If the device functions similarly to elevate the fetal buttocks, it may improve the success rate for the external cephalic version procedure, thus decreasing the risk that pregnant women may need a cesarean delivery. Because this research involves a procedure unique to pregnancy, it requires consent from pregnant patients. Patients unable to understand the consent process are excluded.

Inclusion Criteria

1. Breech presenting part as diagnosed by bedside sonography.
2. Pregnancy is between 37-40 weeks gestational age.
3. Live fetus.
4. Patient is \geq age 18.
5. Patient speaks English or Spanish as primary language.
6. Patient able to understand verbal and written consent

Exclusion Criteria

1. Non-breech presentation (cephalic, transverse, oblique).
2. More than 1 fetus.

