Visit 1 (ECV Procedure): The PI/Sub-I will meet the patient at the labor and delivery area, and review both the ECV procedure and possible study inclusion. The patient and researcher will sign consent forms if the patient qualifies for study inclusion and agrees to participate.

After weighing the patient, calculating a body mass index, performing a digital cervical exam, and performing a fetal non-stress test and obstetric ultrasound, all routine components of the ECV process, the PI/Sub-I will verify there are no exclusion criteria. Assuming that an ECV is still necessary and safe, the patient will receive a 0.25mg subcutaneous injection of terbutaline, a medication to quiet the uterus that is commonly used for ECV procedures. The midwife/physician performing the device inflation or sham inflation will open the randomization envelope. The researchers are blinded to patient randomization. All patients will mark a line on a 100mm VAS to assess pre-procedure pain.

The researcher will show the patient the device, open the sterile container, and insert the device into the vagina per manufacturer's guidelines for all patients in the study. All patients will mark a line on a 100mm VAS to assess post-insertion pain. The study physician will then obtain the assistance of a trained midwife/physician to inflate the device or perform a sham inflation. For the physician to remain blinded, the physician will leave the room during the time of the inflation/sham inflation. This will be documented in the source documents. Midwives/Physicians performing the inflation or sham inflation will have undergone previous training. Inflating the

Fetal Pillow is similar, although less difficult, than other balloon devices commonly used on the labor and delivery unit. The assisting midwife/physician will inflate the device with 180 mL of saline for those patients randomized to inflation. This will occur under a sheet so that the patient is blinded to the randomization scheme. If the patient is randomized to no inflation, the midwife/physician will perform a sham inflation, also under a sheet. All patients will mark a line on a 100mm VAS to assess post-inflation/sham inflation pain. The assisting midwife/physician then leaves the room, and the study physician reenters the room and proceeds with the ECV procedure.

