Regardless of randomization, at this point the ECV procedure proceeds using normal routine. Once completed, all patients will mark a line on a 100mm VAS to assess post-ECV pain. The ECV will be attempted up to four times and VAS will be assessed after each attempt.

The research physician will then remove the Fetal Pillow and perform a post procedural ultrasound to verify fetal position. Regardless of randomization, the procedure is completed per the usual routine of fetal monitoring, assessing for labor or bleeding, discussing post-procedure care, then discharge home (or, less likely, admitting for either observation or delivery).

The researcher will fill out the ECV portion of the data collection form.

Visit 2 (Labor and Delivery): There are no study interventions during this visit. The file linking the subject's FIN and study numbers will be sent to the honest broker who will then extract the data for delivery outcomes for the mother and neonate along with the final cost calculations. This data will be entered into a spreadsheet by the honest broker and then sent back to the research team. The research team will send the file linking the subject's FIN and study numbers at the intervals outlined in the safety monitoring plan (first 10 randomized subjects and every 20 subjects thereafter). The investigators are unblinded to patient randomization after the ECV procedure has been completed and during data collection for delivery and neonatal outcomes.

Data collection for patients delivering outside of AdventHealth facility. Patients will sign a release of records; study coordinator will request records from delivering facility and delivery outcomes data will be imported into spreadsheet linked to FIN.

Study Duration:

Estimated date of study completion: March 31, 2023

- Projected start date: November 1, 2020.
- Projected completion of enrollment of all study subjects: November 1, 2022.
- Projected final data collection date: March 1, 2023.

Materials of Human Origin: N/A

Study Outcome Measures (Endpoints)

Primary Outcome:

Proportion of patients undergoing ECV who have a successful outcome with and without an inflated Fetal Pillow.

Secondary Outcomes:

As noted, many of these data points are normally recorded in the medical record during an ECV procedure and subsequent delivery, regardless of study participation.

Subject Information (maternal):

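### The operator removes the device before the ultrasound that records the primary outcome, so blinding covers the manoeuvre and the pain scores but not outcome assessment

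*Combined protocol and SAP*

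**What the plan says.** Research Design labels the study: "This is a prospective, randomized double-blind clinical trial". Visit 1 (ECV Procedure) adds that the researchers do not know the assignment, and describes how this is achieved: "For the physician to remain blinded, the physician will leave the room during the time of the inflation/sham inflation". A trained assistant opens the envelope and works under a sheet: "The assisting midwife/physician will inflate the device with 180 mL of saline for those patients randomized to inflation". Women assigned to no inflation get a sham. Then: "The assisting midwife/physician then leaves the room, and the study physician reenters the room and proceeds with the ECV procedure".

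At the end of the visit: "The research physician will then remove the Fetal Pillow and perform a post procedural ultrasound to verify fetal position". The device description says only: "After the procedure the device is deflated, removed and discarded". It does not say who deflates it.

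That ultrasound determines the primary outcome (Primary Objective; Procedural Outcomes, item 29). The researcher then completes the ECV part of the data form. Adverse events are collected from insertion to one hour after the ECV, and the Investigator classifies their severity and relatedness (Adverse Event Reporting).

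On the end of blinding, Visit 2 (Labor and Delivery) states: "The investigators are unblinded to patient randomization after the ECV procedure has been completed and during data collection for delivery and neonatal outcomes".

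**The concern.** The protocol takes real trouble to hide the allocation from the operator at inflation, with a second practitioner, a sheet and a sham. It does nothing comparable at removal. The person who removes a device that was filled with 180 mL or left empty is the person who next reads the primary outcome and fills in the form.

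At stake is whether the double-blind label holds for outcome assessment. This matters least for presentation on ultrasound. It matters more for items that need judgement: the amount of bleeding, the fetal heart rate pattern, event severity and device-relatedness. Relatedness also has a consequence outside the analysis. Under Serious Adverse Event Reporting, only serious events judged related to the device go to the FDA and the IRB, although Protocol Deviations sends all serious events to the internal research integrity office.

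**Working it through.** **1. The sequence as written (Visit 1, Adverse Event Reporting)**

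| Step | Done by | Measure hiding the allocation from the physician |
|---|---|---|
| Insertion, then VAS | Physician | Not needed; same for all women |
| Inflation or sham, then VAS | Assistant | Physician out of the room; sheet; sham |
| Up to four ECV attempts, VAS after each | Physician | Assistant has left; nothing disclosed |
| Removal | Physician | None described |
| Ultrasound for the primary outcome | Physician | None described |
| ECV form | Researcher | None described |
| Event severity and relatedness | Investigator | None described |

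**2. Does another section close the gap?** No section brings the assistant back to deflate the device, hides its state at removal, names a blinded second reader or provides for a stored image. Procedural Outcomes lists whether the device was inflated (item 5) alongside the primary outcome (item 29). If the form follows that list, the allocation sits on the same form.

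**3. Does the unblinding sentence help?** Completion of the ECV could mean the end of the last attempt or the end of the whole visit. On either reading, removal is written before the scan, and the sentence does not make disclosure wait for a recorded outcome.

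**4. What comes before and after removal**

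- Before: all VAS scores, number of attempts, forward and reverse rolls, and how the manoeuvre was done.
- After, or recorded after: the confirming ultrasound, bleeding within one hour, hematoma, laceration, the written account of bradycardia and decelerations, and event grading.

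**5. Size for the primary outcome**

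The plan's own figure comes first (Sample Size Determination): 49% versus 73.5%, 80% power, two-sided 5%, 1:1. The mean proportion is (0.49 + 0.735)/2 = 0.6125.

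- n = [1.960·√(2·0.6125·0.3875) + 0.842·√(0.49·0.51 + 0.735·0.265)]² / 0.245² = 60.9
- With continuity correction: (60.9/4)·[1 + √(1 + 4/(60.9·0.245))]² = 68.8, which rounds up to 69 per group, as stated.

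The documents give no misreading rate, so the following is an illustration on assumed rates. Let true success be 49% in both arms, and let a fraction m of true failures in the inflation arm only be recorded as successes. Recorded success in that arm is 0.49 + 0.51·m. The last column is the probability that a two-sided 5% chi-square test (no continuity correction, 69 per arm, exact enumeration) rejects.

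| m (assumed) | Recorded success, inflation arm | Spurious difference (points) | Rejection rate |
|---|---|---|---|
| 0 | 49.0% | 0 | 5.0% |
| 2% | 50.0% | 1.0 | 5.1% |
| 5% | 51.6% | 2.6 | 6.0% |
| 10% | 54.1% | 5.1 | 9.2% |

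The planned difference is 24.5 points. For the judged safety items the documents offer no basis for a figure.

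**The case against.** The strongest reply is that the design blinds what matters most. Bias could change success mainly through how hard or how long the operator tries, and that stage is protected. Pain, the most subjective outcome, is scored by the patient before removal. With up to four attempts allowed, the operator must already have a view of success while the device is in place. The ultrasound then verifies that view, and Sharing of Results with Subjects says the patient knows the result at once. The protocol also states openly that investigators are unblinded after the ECV. All of this stands, and it limits the point to outcome assessment.

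Three further points stand in part.

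- That the physician learns the allocation is an inference, since nobody is named as doing the deflation. It is a strong one: the same person removes the device and no concealment is described.
- Event grading falls to the Investigator, who need not be the operator. But investigators are unblinded by then, so a different grader is not assured to be blind. Some grades do rest on concrete criteria such as transfusion or sphincter injury, and membrane rupture is confirmed by testing.
- Scanning before removal, or having a blinded reader look at a stored image, would be lighter. Either would help only the primary reading, and the documents do not say whether a filled balloon would show on a scan made with it in place.

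A reader might infer that the blind is lost for every outcome, or that the primary result is materially biased. The documents do not support either: the pain scores and procedural counts are fixed before removal, and presentation on ultrasound leaves little room for judgement. A reader might also infer that learning past allocations in a blocked sequence makes later ones predictable. Block size is not given, and the change below would not address that, so it is no part of this point.

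**Conclusion.** The concern holds for outcome assessment only. As written, the primary-outcome scan, the ECV form and possibly the event grading are done by someone who very likely knows the allocation, and the double-blind label does not say so.

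The effect on the primary comparison is probably small. Even at an assumed one-sided misreading rate of 5%, the false-positive rate is 6.0%; reaching 9.2% needs 10%, and nothing in the documents suggests a rate that high. Exposure is greater for bleeding, heart rate pattern, event severity and device-relatedness, but cannot be quantified from the documents.

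This rests on two assumptions: that the steps are carried out in the order written, and that removing the device reveals whether it was filled. Sample size, power and the planned tests are unaffected.

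**What to change.** In Visit 1 and Visit 2 of Study Visits:

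1. Mirror the inflation step. The trained unblinded assistant returns, then deflates and removes the device under the sheet, out of the physician's view. Allow an exception whenever the treating team judges that safety requires otherwise, and record each exception as an unblinding. Amend the device description to name who deflates and removes.
2. Have the physician record the ultrasound result, the ECV form and the initial grading of severity and relatedness before any allocation is disclosed. Have the assistant record the inflated/not inflated item separately.
3. Reword the unblinding sentence so that disclosure follows those records rather than the end of the ECV.
4. If this sequence is not adopted, or for any women already treated under the present one, limit the double-blind claim to the patient and to the operator during the manoeuvre, and report that outcome assessment was not blinded.

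The cost is a few sentences of protocol text, one brief return to the room by an assistant already used in the trial, and a short delay in disclosure. The assistant must be available at the end of the procedure.

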Consent Process: Potential research subjects will be screened for inclusion and exclusion criteria and scheduled for their ECV procedure. [name] or [name] will review the ECV procedure with the subject including the potential risks versus benefits of the Fetal Pillow device. Subjects will also receive written information at the hospital and will sign an informed consent document (HRP 500). At this time subjects will receive a screening number, which will be obtained from the master subject list. Researchers will follow HRP-802 and HRP-803 for guidance when obtaining informed consent. (Declining participation will not impact patient care: patients who do not consent to participate but who also want an ECV procedure will undergo an attempted ECV outside of the study protocol).

Documentation of Informed Consent Process

Documentation of the informed consent process is required to establish that the subject was accurately and adequately informed and that no study-related procedures were initiated prior to obtaining informed consent. A research team member will note in the source documentation the consent process, date and time consent was obtained and that consent was obtained prior to initiating any research procedures.

Non-English Speaking Subjects:

[name] is fluent in Spanish and will consent patients verbally (Spanish) and in writing (consent form written in Spanish).

Subjects who are not yet adults (individuals under the age of 18): N/A

Cognitively Impaired Adults: N/A

Adults Unable to Consent: N/A

Waiver of Consent: N/A

Randomization:

Patients will be randomized 1:1 using a block scheme using statistical software. Randomization assignments will be sealed into sequentially numbered, opaque envelopes which are stored in the locked study cabinet on the labor and delivery unit. A trained unblinded practitioner will obtain the randomization envelope from the locked study cabinet and will note the randomization number on the randomization form. The subject master list will be kept electronically in the Teams files only accessible by Drs. [name], [name] and the research personnel. Only Drs. [name], [name], trained midwives/physicians and research coordinators will have access to the locked study cabinet.

Study Visits:

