Researchers will record the cost of stay for both mothers and babies, for both the ECV procedure and the admission for delivery. This will be obtained from the mother's and child's medical record.

Data Management and Quality Plan

Data De-identification

Data will be de-identified prior to analysis. Each patient will be assigned a 4-digit code that will not contain any unique identifiers. The code will be linked to the patient's FIN which will be stored in a separate file on a password-protected laptop stored in a locked office. The de-identified data will be stored in a similar fashion in a separate file. Drs. [name], [name], the research department personnel and the honest broker will have access to both files. We anticipate that once data is entered for each individual patient, the link will be used only for the purposes of random audits to ensure data accuracy. Once data has been analyzed and results have been published, the link to the de-identified data will be destroyed after 7 years. As the assigned study number will not be linked to any PHI, we do not foresee any possible breach occurring.

Data Confidentiality, Storage, and Retention

Study documentation and paperwork will be stored behind 2 locked doors in the Center for Pediatric & Women's Research Department during the active study period. Upon study closure the paper records will remain in the research office for storage. The data file will be stored electronically on a password protected secure server at AdventHealth accessible only to study team members as listed on the personnel log. Study documentation will be retained for 7 years after study completion. After that period, paper records will be placed in hospital approved shred bins.

Electronic records will be placed in a computer electronic trash bin followed by immediate emptying of the electronic trash bin.

Data Quality

Quality control procedures for this study include source data verification by randomly selecting 10% of subjects (9 if enrollment goal is met) and verifying all values. If more than one discrepancy is found, an additional 10% of subjects will be checked. Based on those findings, additional subjects or all subjects may be verified. The AdventHealth Office of Research Integrity will create a monitoring plan and conduct internal monitoring of the study for patient safety and data integrity.

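### Investigators are unblinded after each version procedure while enrolment continues in blocks at one site, so later allocations may be partly predictable despite sealed envelopes

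*Combined protocol and SAP*

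**What the plan says.** - **Blinding.** Research Design: "This is a prospective, randomized double-blind clinical trial". Visit 1: "The researchers are blinded to patient randomization". The study physician leaves the room while an assistant inflates or sham-inflates the device.
- **Unblinding.** Visit 2: "The investigators are unblinded to patient randomization after the ECV procedure has been completed and during data collection for delivery and neonatal outcomes". The preceding sentence describes file transfers after the first 10 subjects and then after every further 20. Sharing of Results with Subjects delays arm disclosure to patients until the analyses are done. Nothing similar is said for investigators.
- **Randomization.** "Patients will be randomized 1:1 using a block scheme using statistical software". The block size is not given, nor whether it varies or is withheld. "Randomization assignments will be sealed into sequentially numbered, opaque envelopes". "A trained unblinded practitioner will obtain the randomization envelope from the locked study cabinet". Besides two named doctors, "trained midwives/physicians and research coordinators will have access to the locked study cabinet".
- **Data files.** Data De-identification names two doctors and adds that "the research department personnel and the honest broker will have access to both files".
- **Who decides and operates.** Outside obstetric providers start the referral, and a study doctor then contacts the patient (Subject Recruitment and Screening). The PI or sub-investigator checks exclusions. The inflating assistant opens the envelope, a step described after that check. The study physician makes up to four attempts (Visit 1).
- **End of the procedure.** In Visit 1 the research physician removes the device and then scans. The device description has it deflated before removal but does not say by whom.

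**The concern.** A sealed envelope protects only the assignment inside it. In a 1:1 block scheme, each known past arm in the current block shifts the odds for the next one, and the last places in a block can become certain. If the physicians who recruit, check eligibility and operate learn each arm as they go, they can form a view of the next arm before they meet the patient.

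Two decisions are then exposed: whether to enrol her (a woman who declines can still have the procedure outside the study), and how hard to try within the four permitted attempts. The second bears directly on the primary outcome. The direction is unknown. More effort in presumed inflated cases would create a false difference, and more effort in presumed sham cases would hide a real one. Reading of the outcome itself is less exposed, because presentation on ultrasound is fairly objective.

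**Working it through.** **1. The plan's own figure.** Inputs from Sample Size Determination: 49% v 73.5%, 80% power, two-sided 5%. The mean proportion is 0.6125 and the difference is 0.245.

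n' = [1.960 × √(2 × 0.6125 × 0.3875) + 0.842 × √(0.49 × 0.51 + 0.735 × 0.265)]² / 0.245² = 60.9

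With continuity correction: n = (n'/4) × [1 + √(1 + 4/(n' × 0.245))]² = 68.8, which rounds up to the stated 69. Then 69 × 1.10 = 75.9, giving 76 per arm and 152 in total. Study Site/Location gives 138, which is 2 × 69. Both totals are used below, and the difference does not affect this point.

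**2. Unblinding after each patient (upper bound).** Assumptions: fixed block size, known to the guesser, and all past arms known. Block size is assumed because none is stated. Example for a block of 4: the chance of a correct guess is 1/2, 2/3, 2/3 and 1 at the four places, so the mean is 2.833/4 = 0.708. The third place is certain with probability 1/3 and the fourth always, so the certain share is (4/3)/4 = 1/3. In general, for size B = 2m, the certain share is [2m/(m + 1)]/B.

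| Block size | Best guess right | Certain | Of 138 | Of 152 |
|---|---|---|---|---|
| 2 | 75.0% | 50.0% | 69 | 76 |
| 4 | 70.8% | 33.3% | 46 | 51 |
| 6 | 68.3% | 25.0% | 35 | 38 |
| No past arms known | 50% | 0 | 0 | 0 |

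**3. Arms learned only at the transfers (after 10, 30, 50 and so on).** With blocks of 4, each of the eight transfers within 152 subjects falls mid-block, leaving two places open. These are certain with probability 1/3 and otherwise even. Expected certain allocations: 8 × 2 × 1/3 = 5.3. Accuracy: 0.5 + 16 × (1/6)/152 = 0.518. Blocks of 2 give 0.500 and 0 certain. Blocks of 6 give 0.513 and 2.4 certain.

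**4. Varying block sizes.** With blocks of 4 and 6 in random order, and a guesser who knows that menu and every past arm, simulation gives 69% accuracy but only about 6% certain.

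**5. Effect on the result (illustrative only).** Suppose every guess shifts success by s: up for a presumed inflated case, down for a presumed sham case. With accuracy a, the false difference is 2s(2a − 1). For s = 0.05 this is 0.050, 0.042 and 0.037 for blocks of 2, 4 and 6. Type I error at 49% success with no true effect, and power at 49% v 73.5% with the shift reversed, were simulated with 138 women (40,000 trials for type I error). Values are for blocks of 2 / 4 / 6.

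| s | Type I, uncorrected chi-square | Type I, continuity-corrected | Power, uncorrected | Power, corrected |
|---|---|---|---|---|
| 0 | 4.9 / 4.9 / 4.9% | 3.3 / 3.2 / 3.4% | 84.4 / 84.6 / 84.3% | 79.9 / 80.2 / 79.8% |
| 2 points | 5.7 / 5.5 / 5.2% | 3.8 / 3.7 / 3.4% | 77.8 / 79.0 / 79.3% | 72.4 / 73.7 / 74.2% |
| 5 points | 9.1 / 7.7 / 6.9% | 6.5 / 5.3 / 4.7% | 65.0 / 68.9 / 70.9% | 58.5 / 62.5 / 64.9% |

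Fisher's exact test gives type I errors close to the corrected column (6.5 / 5.7 / 4.7% at 5 points).

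**The case against.** **The documents do not contradict themselves on blinding.** A reader might set the double-blind label against the Visit 2 sentence and infer a contradiction. Patient and operator can both be blind during each procedure, and the plan says openly when that ends. It is a disclosed design choice, and the issue is its effect on later patients.

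**Concealment is not shown to have failed.** Referral starts outside the team, many eligibility criteria are measured, the assistant opens the envelope, and the procedure is to follow usual routine in both arms. These safeguards stand and limit selective enrolment. Cabinet access does not by itself reveal past arms: the cabinet holds sealed envelopes, and nothing says opened ones return to it. The data file shows the arm only if it carries item 5 of Procedural Outcomes (whether the pillow was inflated). With names removed, it cannot be confirmed that the doctors with access are those who enrol and operate.

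**The figures stack assumptions.** The documents do not say that blocks are fixed, that investigators know the size, or that anyone would act on a guess. More than one study doctor is mentioned, so a guesser would have to track colleagues' cases too. This is why the percentages are upper bounds. If the transfer schedule governs unblinding, they nearly vanish.

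**Deferral may be unachievable as things stand.** If the physician who removes the device also deflates it, or sees it deflated, the arm may be evident after every case, before the confirming scan, whatever Visit 2 says. This is the strongest objection. It does not remove the concern, but it means the removal step must be settled first.

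**Conclusion.** The point holds conditionally, with medium confidence, and the sponsor should act on it. Read naturally, the plan tells investigators each arm after each procedure during enrolment, and block randomisation makes that knowledge informative. Under a fixed, known block size of 2 to 6 with all past arms known, guess accuracy rises from 50% to between 68% and 75%, and a quarter to a half of allocations become certain. Under transfer-only unblinding, accuracy is 50 to 52%.

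A reader might infer that type I error is 9% or that power is 65%. The documents do not support that, because they give no shift, no direction and no block size. A 2-point shift leaves type I error almost unchanged. The 9% figure needs a 5-point shift on every guess, blocks of 2 and an uncorrected test. The corrected test, which matches the plan's sample size formula, gives 6.5% there. The corresponding power loss (to 65.0%, or 58.5% corrected) needs the same behaviour in the opposite direction.

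**What to change.** 1. **Settle the removal step first.** Reconcile the device description with Visit 1 on who deflates and removes the device, in what order relative to the confirming ultrasound, and whether that person is blinded. No clinical handling is proposed here.
2. **Replace the Visit 2 sentence.** Suggested text: *Physicians who enrol patients or perform ECV are not told any allocation until the last ECV has been completed, unless a named role independent of those physicians decides that a safety need requires it.* The monitors in the Safety Monitoring Plan could fill that role. Amend Randomization, Study Outcome Measures and Data De-identification so that, until then, these physicians have no access to randomization forms, opened envelopes or any file showing the arm. Route delivery data through the honest broker, since the outcome section currently has researchers record them.
3. **Separate form.** Have the already-unblinded assistant record item 5 of Procedural Outcomes on a form kept from those physicians.
4. **Varying block sizes**, not disclosed to enrolling staff. This cuts certain allocations to about 6% with mixed blocks of 4 and 6, but guess accuracy stays near 69%. It supplements step 2 and does not replace it.
5. **Check effort.** Report attempts and rolls by arm from items 28 and 31 to 33 of Procedural Outcomes, which are already collected.

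The cost is one extra form and narrower file access, with the sample size unchanged. The investigator classifies device-relatedness of adverse events. Because the device is inserted in every patient, much of this can be done blinded, and the safety exception covers the rest.
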